6.8.2.2 Clinical Global Impressions - Angelman Syndrome Scales

The CGI-S-AS scale with AS-specific anchors will be used by the investigator to assess the severity of symptoms, and the CGI-I-AS scale will be used by investigators to assess improvement from Baseline. The CGI-S-AS captures specific characteristics commonly present in the AS population; the CGI-I-AS captures clinical impression that reflects the rater's estimate of change from the initiation (Baseline) of treatment. Both the CGI-S-AS and the CGI-I-AS assessments will be conducted by a rater with experience in AS and trained in CGI-S-AS and CGI-I-AS rating by the sponsor. It is highly preferable that each site uses the same rater. Whenever possible, the same rater (the principal investigator) at each site must evaluate a given study participant throughout the study. As an exception, a clinician sub-investigator, trained in CGI-S-AS and CGI-I-AS rating by the sponsor, may be used.

The baseline CGI-S-AS will be accompanied by detailed investigator notes. Each CGI-I-AS rating will also be accompanied by detailed investigator notes [REDACTED]

[REDACTED] To reduce recall bias, within 24 hours prior to the study participant's clinic visit at Week 12 (the first CGI-I-AS assessment), the investigator must review the study participant's baseline CGI-S-AS score and investigator notes. Within 24 hours prior to the study participant's visit at Week 36 (and all subsequent visits with assessments of CGI-I-AS), the investigator must review the study participant's baseline CGI-S-AS score and investigator notes and the prior clinic visit's CGI-I-AS score and investigator notes. If the CGI-I-AS assessment is missing at a study visit, the reason for the absence will be noted in the eCRF.

7 Statistical and Analytical Plan

7.1 Safety Endpoints

The following safety endpoints will be evaluated for study participants who are at least 2 years old at study entry:

- Incidence of SAEs, TEAEs, treatment-related TEAEs, and TEAEs leading to study discontinuation
- Vital sign measurements
- Clinical safety laboratory values
- Physical examination
- Assessment of suicidality (ABC-I; Section 6.2.2.1)
- The 28-day seizure frequency (Section 6.2.2.4)

7.2 Secondary Efficacy Endpoints

The secondary efficacy endpoints below are not listed in order of importance. Efficacy assessments are only to be conducted in study participants who are at least 4 years old at study entry. If a study participant is 2 to 3 years old at study entry and turns 4 years old during the course of the study, only safety assessments are to be continued.

7.2.1 LAR/Caregiver-Completed Endpoints (for Study participants at Least 4 Years Old)

- Change from baseline in the CSHQ total and subscale scores
- Change from baseline in sleep diary parameters:
 - Latency of sleep onset (LSO), defined as time from beginning of rest period to start of sleep onset
 - Sleep efficiency, defined as the percentage of total sleep time out of duration of the rest period
 - Total daytime sleep, defined as duration of sleep time in the active interval

7.2.2 Clinician-Completed Endpoints (for Study participants at Least 4 Years Old)

- CGI-I-AS scores

- Change from baseline in CGI-S-AS scores:
 - The CGI-S-AS symptoms overall score
 - The CGI-S-AS domain scores
- Change from baseline in the VABS-3 overall composite and subscale scores:
 - Communication domain and its subdomains
 - Socialization domain and its subdomains
 - Daily Living Skills domain and its subdomains
 - Maladaptive Behavior domain and its subdomains

7.3 Exploratory Endpoints

The exploratory efficacy endpoints below are not listed in order of importance.

7.3.1 LAR/Caregiver-Completed Endpoints (for Study participants at Least 4 Years Old)

- Change from baseline in PedQoLI total and subscale scores

7.3.2 Clinician-Completed Endpoints (for Study participants at Least 4 Years Old)

- Change from baseline in the VABS-3 Motor Skills domain and its subdomains

7.3.3 Endpoints for Relationship Exploration

- Endpoints of interest may be identified to explore the relationships among them.

7.4 Sample Size Calculations

This is an open-label extension study from 3 prior protocols, and siblings of study participants completing those studies are eligible to enroll; thus, sample size calculation is not based on power calculations. The number of study participants enrolled in the study will be dependent on the number of study participants who are eligible and consent to participate in the extension study. Approximately 170 study participants will be enrolled in the study.

7.5 Analysis Sets

The following analysis sets will be used in the statistical analyses.

Enrolled Analysis Set (EAS): The EAS will consist of all study participants enrolled in the extension study.

Safety Analysis Set (SS): The SS will consist of all study participants who receive at least 1 dose of study drug.

Full-Analysis Set (FAS): The FAS will consist of all study participants who receive at least 1 dose of study drug and have at least 1 post baseline efficacy assessment.

The EAS will be used for summaries of study participant disposition, demographics and other baseline characteristics. All safety evaluations will be carried out on the SS. All efficacy evaluations will be carried out on the FAS.

7.6 Subgroup Analysis

Subgroup statistical analyses may be performed and will be detailed in a statistical analysis plan.

7.7 Statistical Analysis Methodology

The detailed methodology for the summary and statistical analyses of the data collected in this study will be documented in a separate statistical analysis plan.

All statistical analysis will be performed using SAS® software (SAS Institute Inc., Cary, NC) Version 9.4 or higher.

Unless otherwise specified, baseline will be defined as the last non-missing evaluation prior to or on the date that the first dose of treatment is taken in this study.

Descriptive statistics (number of study participants, mean, SD, median, minimum, and maximum) will be presented for continuous variables and frequency and percentage will be presented for categorical and ordinal variables. If there are missing values, the number missing will be presented, but without a percentage. All data collected will be included in by -study participant data listings. Two--sided 95% CIs will be provided where appropriate. Graphical displays will be utilized to investigate trends over time overall and by relevant subgroups as needed.

Separate analyses of selected endpoints, including but not limited to CGI-I-AS, CGI-S-AS, and seizure diary data, will be performed for the study participants who have participated in STARS and the study participants who have participated in the NEPTUNE study (Study OV101-19-001).

7.7.1 Analysis of Primary Endpoints - Safety

All safety analyses will be performed on the SS.

All AEs will be coded using latest version of MedDRA and will be classified by MedDRA system organ class (SOC) and preferred term (PT).

The number and percentage of study participants who experience at least 1 TEAE as well as the 95% exact CI for the incidence of TEAEs overall and within each specific SOC and PT will be presented.

Treatment emergent adverse event is defined as newly or worsening AEs start from the first dose of study medication till 30 days after the last dose of study medication.

Treatment-related AEs will be identified as those that are at least possibly related to study drug based on the investigator's assessment. The number and percentage of study participants with treatment-related AEs, SAEs, TEAEs leading to study discontinuation, and TEAEs leading to death will also be summarized by SOC and PT.

For each SOC and each PT, a study participant will be counted only once for study participant-incidence tabulations. For summaries by severity or relationship, for a given study participant, the highest severity and relationship for a specific PT will be considered.

Descriptive statistics for the observed values and changes from baseline to each post baseline visit with respect to clinical laboratory and vital sign measurements will be summarized. Clinically significant laboratory values may be tabulated.

Shift tables for laboratory parameters will be presented. For each continuous laboratory parameter, results will be categorized as low, normal, and high based on the laboratory normal ranges. Frequencies and percentages will be presented for the shifts in these categories from baseline to each posttreatment assessment timepoint.

Suicidality assessed by ABC-I will be summarized descriptively at baseline and all post baseline study visits. Change from baseline to all post baseline study visits also will be summarized descriptively.

Abnormal findings in physical examinations will be listed.

The 28-day seizure frequencies as captured in the seizure diary will be calculated for baseline and post baseline study periods for all seizure types and for subtypes of drop and nondrop. Percent change in 28-day seizure frequency from baseline to all post baseline study visits will also be summarized descriptively for all seizure types and for subtypes of drop and nondrop.

Concomitant medications will be coded using the World Health Organization Drug Dictionary. A table summarizing concomitant medications and a by-study participant listing of concomitant medications will include all medications taken during the study regardless of the timing for the start of medication.

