The study will comprise a screening period of up to 30 days; a baseline visit on Day 1 for baseline assessments (at which the first dose of study drug will be taken at the site unless a patient is unable to attend a clinic visit in person due to COVID-19 restrictions, in which case the first dose of study drug to be taken at bedtime in the evening of Day 1); and clinic visits for safety and efficacy assessments over a 3-year treatment period. Baseline visits must be conducted on site and not remotely for patients who did not complete an OV101 antecedent study (eg, siblings [with AS] of study participants with AS who have completed previous Ovid studies of OV101). After the baseline visit, the clinic visits will occur at Weeks 12, 36, 64, 96, 128, and 160 (end of treatment [EOT]). If a patient cannot attend an in-person visit, a home visit may be conducted by a trained mobile healthcare professional to perform study assessments e.g. vital signs, body system assessment, clinical labs draws, review/collection of study materials.

Telehealth/virtual visits will occur at Weeks 24, 48, 80, 112, and 144. A follow-up phone safety visit at the EOS will occur approximately 14 days after the last dose of study drug (EOT) to assess safety and tolerability associated with discontinuation of treatment. A home nurse/healthcare professional visit will replace a virtual visit if the latter is not feasible. A study participant will be considered to have completed the study after completing the EOS phone visit.

The following study participants will be required to complete screening and baseline visits (and assessments) to determine eligibility before receiving OV101 under this protocol:

- Study participants who completed OV101-15-001 or OV101-16-001
- Study participants who are siblings of study participants who have completed OV101-15-001, OV101-16-001, or OV101-19-001
- Study participants who completed treatment in OV101-19-001 more than 2 weeks before completing the baseline visit under this protocol (OV101-18-002)

For study participants required to complete the screening and baseline visits, the planned duration of study participation is approximately 3 years (from the start of screening to the EOS visit), or until the study drug is commercially available.

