2.1 Primary Objective

The primary objective of this study is to evaluate the long-term safety and tolerability of OV101 in individuals with AS assessed by the incidence and severity of AEs and SAEs in study participants who are at least 2 years old at the time of enrollment into this study.

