4.2 Withdrawal of Study participants from Study Treatment and/or the Study

Study participants who discontinue treatment during the study will be encouraged by investigators to continue to participate in all scheduled clinic visits and assessments, and study data will be collected for these study participants per protocol.

Discontinuation of a study participant from treatment early (before Week 160) for any reason will initiate procedures for discontinuation of the study participant from the study, including EOT and EOS visits (Section 3.1). For study participants who stopped study treatment early (before Week 160), an EOT visit should be conducted within 2 weeks after the last day of study drug. After completing the EOT visit, an EOS visit should be completed within 2 weeks after completing the EOT visit. The duration of the study is defined for each study participant as the date signed written informed consent is provided through the EOS visit.

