6.2.1.3 Eliciting and Documenting Adverse Events

Adverse events will be assessed beginning at enrollment (date of signed informed consent) and up to 30 days after the last dose of study drug. Adverse events must be followed until resolution or for 30 days after the study participant's last study drug dose, whichever comes first.

After informed consent is obtained, at every clinic, phone and/or home health visit, study participants and their LAR/caregivers will be asked a standard nonleading question to elicit any medically related changes in their wellbeing. They will also be asked if they have been hospitalized, had any accidents, used any new medications, or changed concomitant medication regimens (both prescription and over the counter medications).

In addition to study participant observations, AEs identified from any study data (e.g., laboratory values, physical examination findings) or identified from the review of other documents (e.g., study participant diaries) that are relevant to study participant safety or considered to be clinically significant, in the medical and scientific judgment of the investigator, will be documented on the AE page in the eCRF.

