6.2.2.4 Seizure Diary

The seizure diary is a caregiver-reported clinical outcome assessment measure that captures the total number and duration of seizures. Caregivers will record the number, duration, and type of seizures each day using the paper seizure diary. Please also see Section 6.2.1.1 for AE reporting criteria for these seizure events.

The caregiver will be trained by the site with specific instructions beginning with the screening visit to ensure compliance in recording seizures. The seizure diary will be completed each day during the study, beginning at Screening (Baseline for study participants entering this study within 2 weeks of completing the EOT visit of OV101-19-001) and continuing through the EOT. Seizure diaries will be collected and reviewed by the investigator with the study participant's caregiver for proper recording at specified timepoints (Table 6-1). Seizure Identification Form and Diagnostic Review Forms (SIF/DRF) will be completed by site personnel for every eligible study participant. This information will be faxed or emailed to The Epilepsy Study Consortium (TESC) for review and approval. The SIF/DRF will be used to ensure that the seizures are classified accurately. SIF and DRF forms will be collected for patients who have enrolled/completed the study if feasible.

For the prospective baseline period, the seizure frequency (expressed as a 28-day frequency) will be calculated as

$$(\text{number of seizures}) / (\text{number of days seizures were assessed}) \times 28$$

Seizure frequency calculated through this method will be used to confirm the eligibility.

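### Section 7.7.1 gives TEAEs as crude percentages over each participant's own treatment window; if follow-up is cut short, these understate 160-week incidence for common TEAEs that keep arising

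*Combined protocol and SAP*

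**What the plan says.** Section 2.1 sets the primary objective: to "evaluate the long-term safety and tolerability of OV101 in individuals with AS assessed by the incidence and severity of AEs and SAEs". Section 7.1 lists the matching endpoint as "Incidence of SAEs, TEAEs, treatment-related TEAEs, and TEAEs leading to study discontinuation". Neither names a period over which incidence is measured.

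Section 7.7.1 makes this operational. Its summary measure is "number and percentage of study participants who experience at least 1 TEAE as well as the 95% exact CI for the incidence of TEAEs". This is given for all TEAEs together and by system organ class and preferred term, counting each participant once per term. The TEAE window opens at first dose and closes 30 days after last dose, in line with AE collection "up to 30 days after the last dose of study drug" in Section 6.2.1.3. The denominator comes from Section 7.5: "The SS will consist of all study participants who receive at least 1 dose of study drug".

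Planned treatment is 160 weeks (Section 3.1), but the protocol foresees several ways in which follow-up or the data can stop sooner:
- Section 4.2: "Discontinuation of a study participant from treatment early (before Week 160) for any reason will initiate procedures for discontinuation" from the study. There is no replacement (Section 4.2.3).
- Synopsis, Study Design: participation lasts about 3 years "or until the study drug is commercially available".
- Section 7.7.5: data reviews to support submissions, as needed.
- Section 11.3: the sponsor may stop the study at any time.

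Exposure duration is listed and summarised (Section 7.7.4.2.1) and AE onset time is recorded (Section 6.2.1.4), but no section combines them. Section 7.7 leaves detailed methods to a separate SAP and allows graphs of trends over time as needed.

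**The concern.** Time at risk differs between participants, yet each counts once in the denominator, whether followed for 2 weeks or 160. A first event that would have come after follow-up stopped cannot enter the numerator. Read as a long-term figure, the percentage is then too low for any TEAE that continues to arise, and the exact binomial interval around it gives no warning.

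This matters because the study has one arm and no comparator, so TEAE percentages are its main safety result. Two TEAEs with the same percentage may behave quite differently: one confined to the first weeks, the other accumulating for three years with late follow-up missing. Percentages alone cannot separate these cases.

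**Working it through.** **No figure to reproduce.** The sample of about 170 is not derived (Section 7.4), and the protocol states no expected TEAE incidence, onset pattern or drop-out rate for this study. What follows is a sensitivity calculation.

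**Inputs.** From the protocol: n = 170; T = 1120 days (Table 6-1, Week 160) = 1120/365.25 = 3.066 years; window W = 30/365.25 = 0.082 years. Assumed: annual drop-out of 5%, 10% or 20%, exponential with μ = −ln(1 − annual rate) and independent of events; onset distribution F(t) as below.

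**Formulas.**
- Constant hazard: F(t) = 1 − exp(−λt). With λ = 0.10 a year, F(T) = 26.4%.
- Early onset: F(t) = s[1 − exp(−kt)], k = ln 2/median, with s scaled so that F(T) = 26.4%.
- Expected crude proportion = ∫₀ᵀ μ exp(−μd) F(d + W) dd + exp(−μT) F(T + W).
- Coverage = probability, under Binomial(170, crude), that the Clopper-Pearson 95% interval contains F(T). This treats the percentage as a 160-week estimate.

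**Worked case.** Constant hazard, 20% annual drop-out: μ = 0.2231; exp(−λW) = 0.9918; μ/(λ + μ) = 0.6905; exp[−(λ + μ)T] = 0.3712. Crude = 1 − 0.9918 × [0.6905 × (1 − 0.3712) + 0.3712] = 20.1%.

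**Results with the 30-day window** (drop-out 5/10/20% a year):

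| Onset pattern | True 160-week incidence | Expected crude % | Coverage of the 160-week value |
|---|---|---|---|
| Constant hazard | 26.4% | 25.2 / 23.4 / 20.1 | 0.94 / 0.87 / 0.55 |
| Median 52 weeks | 26.4% | 25.3 / 24.1 / 21.8 | 0.95 / 0.91 / 0.74 |
| Median 26 weeks | 26.4% | 25.7 / 24.9 / 23.3 | 0.95 / 0.94 / 0.87 |
| Median 12 weeks | 26.4% | 26.1 / 25.7 / 25.0 | 0.95 / 0.95 / 0.94 |
| Constant hazard | 14.2% (λ = 0.05) | 13.5 / 12.6 / 10.8 | 0.95 / 0.91 / 0.75 |
| Constant hazard | 6.0% (λ = 0.02) | 5.7 / 5.2 / 4.5 | 0.96 / 0.94 / 0.88 |
| Constant hazard | 3.0% (λ = 0.01) | 2.9 / 2.7 / 2.3 | 0.98 / 0.98 / 0.98 |

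**Data cut without drop-out.** If follow-up is uniform between 1 and 3.07 years, the crude figure is the mean of F(u) over that range (no window): 18.3% for constant hazard, 22.0% for median 52 weeks, 24.6% for 26 weeks and 26.2% for 12 weeks, each against 26.4%.

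**Do the added summaries help?** In 5,000 simulated trials per cell with independent drop-out, Kaplan-Meier at Week 160 averaged 26.3% to 26.6%, with coverage of 0.94 to 0.96, for constant hazard and medians of 12, 26 and 52 weeks at all three drop-out levels. For median onset of 26 weeks, one overall rate drifts with drop-out (11.1, 11.6, 12.6 per 100 participant-years). Interval rates stay near 33, 20, 7.6 and 1.8 (0-12, 12-48, 48-96 and >96 weeks), so the single rate should not stand alone.

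**If drop-out tracks event risk.** Suppose half the participants have both hazards multiplied by 3, or by 5, at 20% annual drop-out. Kaplan-Meier then gives 24.5% or 22.9%, against crude 19.2% or 18.3% and a true 26.4%. It is closer, but no longer unbiased.

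**The case against.** The strongest reply is that the plan does define its period. Section 7.7.1 fixes a window for every participant, and the percentage correctly describes events in that window. No section promises a 160-week cumulative incidence, so coverage of 0.55 is measured against a target the protocol never states. This stands: the percentage is not wrong, and what is missing is a fixed calendar horizon. A reader might infer that the plan has no time frame at all, or that its confidence interval is invalid; the documents support neither.

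A reader might also infer that crude percentages are the only TEAE analysis planned. That cannot be shown, because Section 7.7 defers detail to a SAP that was not supplied. All that can be said is that the protocol does not commit to more.

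The size rests on assumptions. The worst value needs a common event, a constant hazard and 20% annual drop-out together. The Phase 2 discontinuations due to AEs over 12 weeks (placebo 1, once daily 0, twice daily 3) are too few and too short to settle three-year drop-out.

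Kaplan-Meier performs well above because drop-out was simulated as independent. Section 4.2.1 lists serious or intolerable AEs as a withdrawal reason, so dependence is plausible. This too stands, and calls for a sensitivity analysis.

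Finally, a contrast with the seizure diary is tempting, but Section 6.2.2.4 gives the divisor "number of days seizures were assessed" only for the prospective baseline period. It does not show that the plan adjusts seizures for time after baseline, and the point does not rely on it.

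One possible defence fails. Section 4.2 encourages participants who stop treatment to keep attending visits, but the TEAE window still closes 30 days after last dose.

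**Conclusion.** The point holds as a worthwhile, low-cost improvement, not as an error in the stated analysis. The crude percentage is valid for events during actual treatment plus 30 days. It understates 160-week incidence when follow-up is cut short and the TEAE is common and keeps arising. The direction follows from the counting rule, and the 30-day window offsets it only slightly.

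The size is conditional. For a constant-hazard TEAE with true incidence 26.4%, the shortfall is 1.2, 3.0 or 6.3 percentage points at 5%, 10% or 20% annual drop-out, and about 8 points for the illustrated data cut. It is 0.7 points or less for a 3% event, and 1.4 points or less when median onset is 12 weeks. At 5% drop-out every tabulated row keeps coverage of 0.94 or more. Drop-out and onset are assumed throughout; confidence is medium, mainly because the SAP was not available.

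**What to change.** In Section 7.7.1, or in the SAP with a cross-reference:

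1. Keep the crude percentage and its exact interval, label it as on treatment plus 30 days, and show median exposure beside it.
2. For any TEAE, SAEs, treatment-related TEAEs, TEAEs leading to discontinuation and seizure TEAEs, add exposure-adjusted incidence per 100 participant-years (time to first event or end of the TEAE window) with exact Poisson confidence intervals, and rates by interval, for example 0-12, 12-48, 48-96 and >96 weeks. State that the single rate assumes a roughly constant hazard.
3. For selected common TEAEs, add Kaplan-Meier cumulative incidence with numbers at risk at weeks that follow-up actually reaches, for example 48, 96 and 160. State that it assumes drop-out unrelated to event risk.
4. As a sensitivity analysis for item 3, add a cumulative incidence function with discontinuation as a competing event.

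If the SAP already contains these, a cross-reference is enough.

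The cost is a few more tables from data already collected, with no change to conduct. Late intervals will be sparse for rarer events, and late estimates less precise: of 170 participants, 170 × (1 − annual rate)^3.066 leaves about 145, 123 or 86 in follow-up at Week 160 with 5%, 10% or 20% annual drop-out.

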A randomized, double-blind, placebo-controlled Phase 2 study (OV101-15-001, STARS; NCT02996305) evaluated the safety, tolerability, and efficacy of OV101 in adolescents and adults with AS over 12 weeks of treatment (Bird et al 2019). Eighty-eight participants with AS (13 to 49 years old) were randomly assigned to 1 of 3 groups: once-daily (QD) dose of OV101 nightly (15 mg), twice-daily (BID) dose of OV101 (10 mg morning and 15 mg night), and placebo. The safety and tolerability of OV101 from Baseline to Week 12 was evaluated by comparing the frequency and severity of adverse events (AEs) and serious AEs (SAEs) in the OV101 treatment groups to those in the placebo group. OV101 was generally safe and well tolerated, with a similar incidence of AEs across all treatment groups: most AEs were mild. Treatment discontinuations due to AEs were low (placebo, 1; OV101 QD, 0; OV101 BID, 3). The most frequent AEs across all treatment groups were vomiting, somnolence, irritability, aggression, pyrexia, and upper respiratory infection. The AEs occurring in the OV101 treatment groups with greater frequency than placebo were pyrexia, rash, seizure, enuresis, myoclonic epilepsy, otitis media, and viral infection. Two study participants had an SAE of seizure: 1 study participant in the BID group deemed "Possibly Related" and 1 study participant in the QD group deemed "Not Related."

This open-label study (OV101-18-002) will evaluate the long-term (160-week) safety and efficacy of OV101 in study participants with AS who either have completed previous Ovid studies (OV101-15-001, OV101-16-001, or OV101-19-001) or are siblings (with AS) of study participants with AS who have completed previous Ovid studies of OV101.

2 Study Objectives and Assessments Related to Endpoints

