Notes: At the investigator's discretion, study participants may be evaluated at unscheduled clinic visits for reasons related to study participant safety. At unscheduled visits, study participants will be queried about adverse events, changes in concomitant medications, and suicidality; and safety laboratory assessments may be conducted. Efficacy assessments will be only for study participants who are at least 4 years old. If study drug is dispensed at unscheduled visit, dosage should be maintained at the same level as at the previous scheduled visit. If a down-titration is required for a clinical indication, this must be discussed with the medical monitor prior to making the change or at the earliest opportunity. Up-titration should not be performed at an unscheduled visit.

^a For study participants entering this study within 2 weeks of completing the EOT visit of OV101-19-001, the screening activities can be verified or conducted at the baseline (Day 1) visit.

^b If the screening and baseline visits can be completed within 14 days, the following assessments do not need to be repeated at the baseline visit: medical history, clinical assessment, physical examination, clinical laboratory tests, and determination of concomitant medications. For study participants entering this study within 2 weeks of completing the EOT visit of OV101-19-001, the EOT visit activities need not be repeated.

^c If a study participant could not attend an in person visit, a telehealth/virtual or home visits, may be conducted by a trained mobile healthcare professional to perform study assessments e.g. vital signs, body system assessment, clinical labs draws, review/collection of study materials. Baseline visits must be conducted on site and not remotely for patients who did not complete an OV101 antecedent study (eg, siblings [with AS] of study participants with AS who have completed previous Ovid studies of OV101).

^d An ET study participant should complete both EOS and EOT visit assessments.

^e Screening is to be conducted for up to 30 days (inclusive) before Day 1; study participants who meet all entry criteria can start treatment at any time during the screening period.

^f There is no Day 0.

^g Signs and symptoms of AS.

^h Review documentation of previous molecular AS testing from the OV101-15-001, OV101-16-001 study, or OV101-19-001.

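### Percent change in 28-day seizure frequency, taken from a baseline diary with no minimum length, shifts in either direction when nothing has changed and leaves out participants with no baseline seizures

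*Combined protocol and SAP*

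**What the plan says.** Section 7.7.1 plans two diary summaries, each for all seizures and for drop and nondrop types. The first is the rate itself: "The 28-day seizure frequencies as captured in the seizure diary will be calculated for baseline and post baseline study periods for all seizure types". The second is the change: "Percent change in 28-day seizure frequency from baseline to all post baseline study visits will also be summarized descriptively". Section 7.7 says what descriptive means: "Descriptive statistics (number of study participants, mean, SD, median, minimum, and maximum) will be presented for continuous variables". It adds: "All data collected will be included in by -study participant data listings".

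Section 6.2.2.4 defines the rate: "For the prospective baseline period, the seizure frequency (expressed as a 28-day frequency) will be calculated as" seizures divided by days assessed, times 28. It gives no minimum number of days, and no section says what to do when the baseline count is zero.

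Baseline length depends on the route of entry:

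- **Screened participants.** Screening lasts up to 30 days, and under Table 6-1, footnote e, "study participants who meet all entry criteria can start treatment at any time during the screening period".
- **Rollovers within 2 weeks of OV101-19-001 EOT.** Section 6.2.2.4 has the daily diary "beginning at Screening (Baseline for study participants entering this study within 2 weeks of completing the EOT visit of OV101-19-001"). Section 3.1 carries over that study's EOT laboratory results, and the Section 13 addendum its last-visit data. Neither mentions seizure diaries.

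Seizures also reach the analysis as adverse events. Section 6.2.1.1 requires an AE for a clear rise over the participant's own baseline, a new seizure type, status epilepticus, or when the investigator thinks it warranted. Section 7.7.1 tabulates TEAEs by SOC and PT with exact 95% confidence intervals. Section 7.7 leaves detailed methods to a separate SAP, which is not part of the supplied text.

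**The concern.** Seizures are a known question for this drug. Section 1 reports that the AEs occurring on OV101 with "greater frequency than placebo were pyrexia, rash, seizure, enuresis, myoclonic epilepsy" and others, and it describes two seizure SAEs on OV101. This study has no control arm, so each participant's own baseline is the only comparator for the diary.

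Three features make percent change a poor summary here:

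1. The denominator is a count over a period that may be short. Its chance error enters the ratio nonlinearly and does not average out.
2. Participants with no seizures in the baseline diary have no percent change. A new onset of seizures on treatment therefore never enters that table.
3. A mean or median does not show how many participants got worse.

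At stake is whether the diary tables can be read at all: a shift in either direction could be an artefact of diary length.

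**Working it through.** **Plan's own figure.** There is none to reproduce. Section 7.4 says the size of about 170 is not power-based, and no seizure rate or margin is given.

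**Inputs.**
- Rate formula: count / days x 28 (Section 6.2.2.4).
- Baseline days d: at most 30, no minimum (Table 6-1). I take 7, 14, 28 and 30. Seven days is an assumption; Section 6.1.1 asks for at least 7 days of sleep diary, which is not a rule for the seizure diary.
- True rate L per 28 days: assumed 1 to 12. The upper end follows from Section 4.1.2, which excludes more than 3 shorter seizures per week (3 x 4 = 12). Zero is allowed.
- Follow-up: 84 days (to Week 12), same rate as baseline, Poisson counts.

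**Step 1: the formula alone.** Three seizures in 7, 14 or 30 days give 3/7 x 28 = 12.0, 3/14 x 28 = 6.0 and 3/30 x 28 = 2.8. With 0 diary days the baseline is 0/0.

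**Step 2: mean percent change when nothing changes.** Let X be the baseline count, Poisson with mean m = L x d/28. Percent change exists only if X > 0, and its mean is 100 x (m x E[1/X | X > 0] - 1). For L = 4 and d = 7, m = 1. P(X = 0) = 0.368 and E[1/X | X > 0] = 0.767, so the mean is 100 x (0.767 - 1) = -23.3%. In full:

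| L per 28 days | d = 7 | d = 14 | d = 28 | d = 30 |
|---|---|---|---|---|
| 1 | -76.5% | -56.1% | -23.3% | -19.4% |
| 2 | -56.1% | -23.3% | +15.3% | +18.6% |
| 4 | -23.3% | +15.3% | +31.9% | +31.3% |
| 12 | +29.8% | +24.7% | +10.3% | +9.4% |

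Two effects compete. When few seizures are expected, requiring at least one inflates the baseline, which looks like improvement. When more are expected, averaging 1/X inflates the ratio, which looks like harm. The median moves too: at L = 4 it is -25% for d = 7 and 0% for d = 28 (simulation, 400,000 draws).

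**Step 3: rates that differ between participants** (gamma, mean 4, CV 1; 1,000,000 draws).

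| | d = 7 | d = 14 | d = 28 | d = 30 |
|---|---|---|---|---|
| Mean | -15.3% | +3.3% | +12.1% | +12.5% |
| Median | -31.7% | -16.7% | -5.6% | -4.8% |
| Zero baseline, no percent change | 50% | 33% | 20% | 19% |
| Zero baseline, seizures later | 43% | 27% | 14% | 13% |

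**Step 4: hidden worsening.** If a fraction f worsens by w% and the rest improve by r%, the mean is f x w - (1 - f) x r.
- f = 0.20, w = 100, r = 25: 20 - 20 = 0%; median -25%.
- f = 0.20, w = 100, r = 50: 20 - 40 = -20%; median -50%.
- f = 0.20, w = 250, r = 50: 50 - 40 = +10%; median still -50%.

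The mean reacts once the worsening is large. The median does not.

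**Step 5: do the alternatives behave?** With no true change, mean absolute change in 28-day frequency stayed within 0.01 seizures of zero at every diary length, and a rate ratio with a diary-day offset stayed at 1.00. Counts of worsened participants need care. At L = 4 with a 28-day baseline, about 41% of unchanged participants reach +50% in at least one of the six intervals ending at Weeks 12 to 160. In the first 84 days alone, about 17% appear to double.

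**The case against.** The strongest reply is that percent change is one part of the seizure assessment. A reader might infer that seizure safety rests only on an average percent change. The documents do not support that. Individual worsening is an AE trigger, and TEAEs are counted by PT with exact intervals. The diary rate itself is summarized, with median, SD, minimum and maximum, and every participant is listed. In the first example of Step 4 the table would show a maximum of at least +100% and an SD of 50 (125 x square root of 0.2 x 0.8). Section 6.2.1.1 has diaries evaluated together with SAEs, and Section 11.1.1 provides an external safety committee.

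This stands, and it limits the point to the diary analysis. It does not remove it. The AE trigger has no numerical threshold and relies on judgment against the same short or absent baseline. A maximum shows one participant, not how many, and a listing is not an analysis.

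It is also fair that the rates, the Poisson model and the diary lengths are assumptions, and that the separate SAP may already add detail. But Section 7.7.1 names the summary measure, and that measure misleads if applied as written. Finally, a count of worsened participants is itself noisy (Step 5). That argues for careful wording of the count, not for leaving it out.

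**Conclusion.** The point holds for the diary-based percent change. With no true change, its mean ranges from about -77% to +32% across the assumed rates and diary lengths. At 4 seizures per 28 days with a 7-day baseline, 37% of participants have no percent change at all. For rollovers within 2 weeks, Section 6.2.2.4 leaves about zero pre-dose days, while Section 7.7.1 asks for change from a baseline period; the two must be reconciled.

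The size rests on Poisson counts, nonzero baselines for the percent change, and assumed rates and lengths. Real diaries are likely to be more variable.

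Two further inferences go too far. One is that the error always reassures: its direction depends on rate and diary length. The other is to turn the 20% example into 34 of 170 participants: the documents do not say how many will have baseline seizures, and seizure-free participants may enroll. Nor do the documents say that a mean near zero would be read as absence of seizure risk. This should be corrected before the analysis, but it does not undermine the study's AE-based primary assessment.

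**What to change.** In Section 7.7.1 or the SAP:

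1. Summarize change over time as a rate ratio from a count model that allows for overdispersion and within-participant correlation, with log(diary days) as offset and zero-baseline participants included. Show absolute change in 28-day frequency beside it.
2. Show percent change only for participants with a nonzero baseline and a stated minimum number of baseline diary days.
3. For each post-baseline period separately, and with the same diary minimum, give the number and percentage (exact 95% CI) with increases of at least 50% and at least 100%. Do not pool these as a rise in any period. Report separately the zero-baseline participants who have seizures on treatment. State that chance variation and regression to the mean will flag some unchanged participants.
4. Reconcile Section 6.2.2.4 with Section 7.7.1 for rollovers, for example by stating whether OV101-19-001 diary data serve as baseline and, if so, from which period of that study.

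The cost is a little more analysis work and fewer participants in the percent-change table. Items 1 to 3 use data already planned for collection; item 4 may require linking diary data from OV101-19-001.
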